7.2.2 Participant Identification Log

Participants recruited to the study will be documented within the participant identification log, which will include the following information:

- Participant name
- Participant initials
- Screening number
- Subject number
- NHS number
- MRN (medical record number)
- Confirmation of eligibility
- Date of consent
- Personal details (address, phone number, email address)
- Withdrawal (yes, no/when and why)

The researcher will use a checklist to determine clinical eligibility. If recruited, patients will be assigned a Case Report Form (CRF).

7.3 Consent

Participants eligible for the study will be sent a PIS alongside a standard anorectal physiology PIL and appointment letter.

The eligible participants will then receive a telephone call from the study team (GI physiology team, who are the patient's direct care team) and will be asked whether they would like to participate. If they would like to participate an appointment will be made which includes both the research study elements and standard care.

At the appointment the researcher will outline what the research study entails, what risks are involved, and they will give the participant an opportunity to ask questions and have them answered satisfactorily. If the participant agrees to participate at that stage the researcher will continue with the informed consent process and complete the Participant Consent Form (PCF). Once the consent form has been signed by both the participant and the researcher, the appointment will proceed. A copy of the consent form will be given to the participant, and the original copy will be stored in the site file. Participants can withdraw their consent at any point during the study, including after data has been collected.

7.4 Randomisation

All participants will have the rectal barostat test, but the order of tests will be changed per patient to avoid bias on the order of tests influencing the results. Patients will either receive procedure A or procedure B:

- Procedure A: Anorectal manometry, elastic balloon distension, endoanal ultrasound, rectal barostat
- **Procedure B**: Rectal barostat, endoanal ultrasound, anorectal manometry, elastic balloon distension

The basic details (e.g. short title, study overview) of the study will be registered with the online randomisation software, Sealed Envelope (https://www.sealedenvelope.com/). The simple randomisation service for non-commercial clinical studies will be selected. At each site a secure NHS email address accessible only to the research team will be used to perform each randomisation. The unique participant randomisation number will be entered into the software. The software will then automatically randomise to procedure A or procedure B. A copy of the randomisation is also automatically emailed. The email containing the randomisation allocation will be printed out and saved as part of the SIF.

Randomisation will occur once informed consent has been obtained and the study eligibility of the participant has been confirmed.

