The most common assessment of rectal sensitivity in a clinical environment is made by gradually inflating an elastic balloon within the rectum, and measuring the volumes at which the patient reports their first sensation, their normal urge to defecate, and sustained urgency^[7]. This is commonly performed in conjunction to anorectal manometry (ARM), which involves insertion of a catheter into the anorectum, and measuring pressure at rest and during specific manoeuvres to assess the function of the anal sphincters^[8]. Most commercially available catheters for this test also contain the required elastic balloon to assess rectal sensitivities, which can be inflated manually or automatically by the equipment, depending on the model and the manufacturer. The advantages of assessing rectal sensitivities using the elastic balloon in conjunction with ARM is that it is fast and cheap, as it does not require a separate catheter being inserted for the additional test. However, the elastic properties of the balloon mean it is unsuitable to assess rectal compliance^[9]. In our

Study protocol: Assessing rectal sensitivity with elastic balloon distension versus rectal barostat.

services, we use two anorectal manometry systems across NUTH and CDDFT services. In NUTH we use a Laborie Solar High Resolution Manometry System with water-perfused catheters, and in CDDFT we use a Medtronic 3D Solid-State High Resolution Manometry System. Both systems are commercially available across the UK, and use a similar elastic balloon for inflation, however, they utilise different published normal ranges of sensory thresholds.

The rectal barostat is another, more comprehensive, device used to assess rectal sensitivity. It contains a polyethylene bag, which is inserted into the patient's rectum and inflated using a pneumatic pump either continuously or in phasic intervals^[10]. Unlike the elastic balloon, the rectal barostat bag has infinite compliance whilst filling, which allows measurement of rectal compliance and total rectal volume, due to its ability to measure opposing pressure of the rectal wall. This protocol is more time-consuming, and for this reason is not routinely used in clinical practice, however it is considered the gold-standard of assessing sensory thresholds, and has the advantage of adding additional information about the biomechanical properties of the rectal wall^[3].

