5.0 STUDY SETTING

Multicentre study. Research sites include:

- Newcastle Upon Tyne Hospitals NHS Foundation Trust (NUTH): Royal Victoria Infirmary, Medical Physics.
- County Durham and Darlington NHS Foundation Trust (CDDFT): University Hospital of North Durham, Medical Physics.

Patients identified at each site will undergo the study at the same site. Therefore, patients are not expected to travel between sites.

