6.3 Number of Participants

In total 30 participants will be recruited for the study. 15 participants will be recruited at NuTH and 15 at CDDFT. Study recruitment will continue until complete study data has been obtained from 15 participants at each site.

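### Test order is randomised by a method described only as a simple service, with no ratio, blocks or site stratum stated, so with 15 patients per site the two orders can end well out of balance

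*Protocol*

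**What the plan says.** Protocol section 7.4 (Randomisation) gives every participant both tests and randomises their order. In Procedure A the elastic balloon comes before the barostat; in Procedure B the barostat comes first. The stated purpose is that "the order of tests will be changed per patient to avoid bias on the order of tests influencing the results". On method, the section says "The simple randomisation service for non-commercial clinical studies will be selected" and "The software will then automatically randomise to procedure A or procedure B". It states no allocation ratio, block size or stratification factor.

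Section 6.3 (Number of Participants) fixes the size: "15 participants will be recruited at NuTH and 15 at CDDFT". Dropouts are replaced: "Study recruitment will continue until complete study data has been obtained from 15 participants at each site".

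Site and balloon system coincide. Sections 1.0 and 7.5.3 place the Laborie system at NUTH and the Medtronic system at CDDFT, and section 5.0 says "Patients identified at each site will undergo the study at the same site". One of the secondary objectives in section 3.2 is to find which of the two systems aligns better with the barostat.

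**The concern.** Randomising order protects a within-patient comparison of two tests only so far as the two orders are about equally frequent. Both tests distend the rectum in one appointment, and section 7.5.3 adds two further balloon sensitivity runs to the standard one. Accommodation or sensitisation from the first test is therefore plausible, and the sponsor itself treats order as a possible source of bias.

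Unrestricted allocation balances orders well in large groups but not reliably in groups of 15. Two results are exposed. Within a site, an unequal split leaves part of any order effect in the balloon-barostat comparison. Between sites, different splits put part of it into the Laborie versus Medtronic comparison. The allocation method has to be settled before the first patient. A later analysis can adjust for order, but it cannot restore the precision lost to a poor split.

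**Working it through.** **Inputs.** 15 participants per site at two sites (section 6.3); 15 + 15 = 30 agrees with the stated total. Two orders, A and B (section 7.4). Assumptions: a 1:1 ratio, since none is stated; unrestricted allocation, which is one reading of section 7.4; and 15 randomised per site. The protocol gives no size for an order effect, so bias is shown as a fraction of it.

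**Split at one site.** The number in Procedure A is Binomial(15, 0.5), and 2^15 = 32,768.
- 10:5 or worse: 2 × (3003 + 1365 + 455 + 105 + 15 + 1) / 32,768 = 2 × 4944 / 32,768 = 0.302.
- 11:4 or worse: 2 × 1941 / 32,768 = 0.118.

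**One or both sites.** 1 − (1 − p)²:
- 10:5 or worse: 1 − 0.698² = 0.512.
- 11:4 or worse: 1 − 0.8815² = 0.223.

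**Gap between sites in Procedure A counts.** Summing over two independent Binomial(15, 0.5) counts gives 0.200 for a gap of 4 or more and 0.099 for 5 or more. The expected absolute gap is 2.2 patients.

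**What an unequal split leaves behind.** Let d be the true barostat minus balloon difference and p the shift from first to second test. The observed difference averages d + p in order A and d − p in order B. With a patients in A and b in B, the site mean is d + p(a − b)/(a + b).
- 11:4: (11 − 4)/15 = 0.47 of p.
- 10:5: 5/15 = 0.33 of p.
- 8:7: 1/15 = 0.07 of p.

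**Percent agreement, the measure in section 7.8.** A site's expected agreement is the average of its agreement under A and under B, weighted by the shares in each order. If the A-to-B gap in agreement is the same at both sites, the system comparison is shifted by (difference in Procedure A shares) × (that gap). A gap of 4 patients is 4/15 = 27% of it; a gap of 5 is 5/15 = 33%.

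**After the change.** With blocks of 2 and 4, every block has an even length, so the 15th allocation falls at position 1 of a block of 2, or position 1 or 3 of a block of 4. At each of these the counts differ by exactly 1. Each site therefore ends 8:7 or 7:8, and the sites' Procedure A counts differ by at most 1, or 1/15 = 6.7 percentage points.

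**The case against.** The strongest reply is that the quoted sentence may name a level of service offered to non-commercial studies and not unrestricted allocation. The protocol does not settle this, and the probabilities above apply only on the second reading. On either reading the method is unstated, so the request to state it stands.

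Three stronger readings are tempting, and the document does not support them.
- *Order is confounded with system.* Order is randomised, so any association with site is partial, arises by chance and has expected value zero. What is completely confounded is system with site, and stratifying the order does not touch that.
- *Order is ignored in the analysis.* Section 7.8 contains no comparison by order, but a statistical analysis plan may exist and could add one. Its absence from section 7.8 is not an error.
- *The benefit of randomising is lost.* Under unrestricted allocation of 15, the root-mean-square residual weight is 1/√15 = 0.26 of the shift, against 1.0 if every patient had the same order. Most of the protection remains on average. An order-adjusted estimate is also still possible at 11:4, with variance (1/11 + 1/4)/(1/7 + 1/8) = 1.27 times that at 8:7.

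It is also fair to say that unrestricted allocation is harder to predict. Section 7.1 has the usual care team do both the screening and the study procedures, so small blocks within site carry some risk of foreknowledge. That is a real cost, but a limited one if block sizes vary. Finally, this is a feasibility study with no primary outcome measure. That lowers the stakes, though it does not explain leaving the method open.

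**Conclusion.** The point holds in a limited form. Section 7.4 randomises order for a stated purpose but does not specify a method that secures it at 15 patients per site. If allocation is unrestricted 1:1, a 10:5 or worse split at one or both sites is about as likely as not (51%). An 11:4 or worse split has probability 22%, and a between-site gap of 4 or more has probability 20%. At 11:4, 47% of any first-to-second-test shift remains in that site's balloon-barostat difference.

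These figures rest on the assumed ratio, on the unrestricted reading of the service, and on exactly 15 randomised per site. They describe how much of an order effect would remain, not how large that effect is; it could be negligible. The improvement is cheap and worth making before recruitment, but its absence does not invalidate the study.

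**What to change.** In section 7.4, state 1:1 allocation in permuted blocks of varying size (for example 2 and 4), stratified by site. Among 15 randomised per site this gives 8:7 and leaves about 7% of any shift. Replacing dropouts under section 6.3 may move the split among completers slightly.

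Optionally, report percent agreement by test order, in section 7.8 or in the statistical analysis plan. This is useful even with balanced orders, because a shift can move patients across diagnostic cut-offs in either order and balance does not cancel that. A mixed model of volumes in mL is not needed: section 7.8 plans no balloon-versus-barostat comparison of volumes, and section 2.0 notes that the devices differ in physical properties and shape at the same volume.

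The cost is a sentence in the protocol and a randomisation set-up with blocks and strata. The protocol does not say whether the chosen service offers these, so the sponsor should confirm it. Allocation becomes slightly more predictable to the team performing the tests; varying the block size, and not disclosing the sizes to that team, limits this. The change does not separate system from site.

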7.5 Assessments

7.5.1 Digital Rectal Examination

Digital rectal examination will be performed before anorectal physiology appointments begin as per standard care and according to local procedure.

7.5.2 Endoanal Ultrasound

Participants from NUTH will have endoanal ultrasound performed as per local procedure using a BK3000 system with a 20R3 9052 transducer. Participants from CDDFT will have endoanal ultrasound performed as per local procedure using a BK Specto system with a 20R3 9052 transducer. Endoanal ultrasound will be performed as per standard care.

7.5.3 Anorectal Manometry and Rectal Sensitivity Testing

Participants from NUTH will have anorectal manometry and rectal sensitivity tests as per local procedure using a Laborie Solar High Resolution Manometry System with water-perfused catheters. Participants from CDDFT will have anorectal manometry and rectal sensitivity tests as per local procedure using a Medtronic 3D Solid-State

High Resolution Manometry System. These tests are performed as per standard care, however rectal sensitivity testing will be performed twice more as part of non-standard care.

7.5.4 Rectal Barostat

Participants from NUTH and CDDFT will have the rectal barostat test performed as per local procedure as part of non-standard care.

7.5.5 Rectal Sensitivity Testing Questionnaire

Participants will receive a questionnaire at the end of their appointment to assess their tolerability to each test. This will take 5 minutes to complete post-appointment to be completed in the waiting room and handed to reception. The completed questionnaires will be collected by a researcher post-clinic.

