Once sensory thresholds have been measured, a diagnosis of normal, rectal hypersensitivity, rectal hyposensitivity, or borderline hyposensitivity is made according to the London Classification disorders of rectal sensation^[11]. In this study we aim to identify whether patients receive the same diagnosis, according to the London Classification, regardless of whether the elastic balloon distension or rectal barostat is used. To achieve this, patients attending for their standard rectal sensitivity tests using the elastic balloon will be invited to repeat their study using the rectal barostat, and the diagnosis they receive (normal, hypersensitive, hyposensitive, borderline hyposensitive) will be compared. From this data, an indication of the clinical utility of the rectal barostat can be suggested, depending on whether a patient's diagnoses changes. As well as this, participants will be offered a questionnaire following their clinic appointment, which will include questions on their tolerability of each test, in order to gather information on the feasibility of a larger cohort study in the future.

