2.1 Assessment and Management of Risk

There are some unavoidable burdens and risks to participants that will be explained fully in the Participant Information Sheet and prior to receiving informed consent to partake in the study. There is first the burden of time required from the patient, which is approximately 30 minutes additional to their standard anorectal physiology appointment time. To minimise this burden, the additional barostat test will be performed at the same time as their standard care appointment, to avoid additional travel costs and time. The barostat test also carries a risk of pain, discomfort, bleeding, and perforation of the rectum (<1 in 1000), the same as standard rectal sensitivity testing using the elastic balloon, which the patients will also be undergoing as part of their standard anorectal physiology appointment. To minimise pain and discomfort, lubrication is used to insert the catheter and the participant advised they can withdraw their consent at any point, and the test will be abandoned. To minimise the risk of bleeding, the test will be abandoned if there is any resistance during insertion of the catheter and participants are excluded from the study if they suffer from excessive or unexplained rectal bleeding. Any participants with risk factors of rectal perforation, such as previous pelvic surgery, pelvic radiotherapy, or inflammatory bowel disease are excluded from the study (according to exclusion criteria), and the barostat automatically deflates if pressure of the rectal wall exceeds 40 mmHg.

This trial is categorised as Type A (no higher than the risk of standard medical care).

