3.3 Outcome Measures

As this is a feasibility study, there are no primary outcome measures, only secondary outcome measures. These include:

- The London Classification diagnoses of each patient when rectal sensitivities are assessed using Laborie system elastic balloon distension versus the rectal barostat, and Medtronic system elastic balloon distension versus the rectal barostat.
- Percentage of rectal capacity at each sensory threshold per test will be measured to assess repeatability
- Total rectal volume (mL) measured using the rectal barostat will be recorded to assess correlation between capacity and balloon inflation (mL) at sustained urgency.
- The number of patients who were eligible to participate in the study.
- The number of patients who chose to participate in the study.
- The number of patients who dropped out of the study.
- The length of time required for the rectal barostat protocol and the elastic balloon distension protocol in clinic
- Costings of rectal barostat test comparison (costs of barostat bags and any additional staff time required)
- Study acceptability and tolerability assessment.

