7.6 Withdrawal

Participants may withdraw from the study at any point. If this occurs, the reason for withdrawal if provided by the participant will be documented in the participant's CRF and the Study Recruitment log. Any study related identifiable information will be destroyed (not including the consent form). However, non-identifiable study information up to and including the point of withdrawal will be retained.

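### Stopping a test for pain is described only as withdrawal of consent, and tolerability is asked once at the end of the visit, so people who could not tolerate a test are likely to be missing from the tolerability outcome

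*Protocol*

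**What the plan says.** Section 3.3 of the protocol lists "Study acceptability and tolerability assessment" among the outcomes. It also says that there is no primary outcome, so the listed outcomes carry the feasibility objective.

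The instrument is a single form. Section 7.5.5: "Participants will receive a questionnaire at the end of their appointment to assess their tolerability to each test". Section 1.0 puts it similarly: "participants will be offered a questionnaire following their clinic appointment, which will include questions on their tolerability of each test".

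For pain and discomfort, section 2.1 gives lubrication and then this: "the participant advised they can withdraw their consent at any point, and the test will be abandoned". The same section has a second, staff-led reason to abandon a test: "the test will be abandoned if there is any resistance during insertion of the catheter". That one is not described as withdrawal.

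Section 7.6 governs what happens after withdrawal: "non-identifiable study information up to and including the point of withdrawal will be retained". On the cause, it says that "the reason for withdrawal if provided by the participant will be documented in the participant's CRF and the Study Recruitment log".

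Section 6.3 sets 30 participants, 15 per site, and keeps recruitment open until each site has 15 complete data sets. Section 3.3 counts drop-outs as a separate outcome: "The number of patients who dropped out of the study".

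**The concern.** The protocol has no category for a participant who asks to stop one test but is willing to stay in the study. If staff follow section 2.1 as written, a request to stop because of pain is handled as withdrawal of consent. The questionnaire falls after that point, and section 7.6 provides for no data beyond it. Section 6.3 then fills the place with someone who completes.

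The tolerability outcome is meant to tell a definitive study how many patients can manage the barostat. The people most informative on that question are those who could not, and these rules tend to leave them out. What remains is closer to tolerability among those who tolerated the tests.

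Merging the two events has a second effect. Under section 11.8.2, withdrawal of consent after the barostat also keeps the result from the referrer and the patient record. Discomfort during a test and refusal of the research are different events, and the protocol gives them one label with one set of consequences. Ratings not collected in clinic cannot be recovered later by any analysis plan.

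**Working it through.** There is no figure in the protocol to reproduce. The only related number is the sample size, 15 + 15 = 30, which has no formula behind it. The check is therefore a reading of the rules in sequence, followed by an illustration with assumed values.

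**The rules in sequence**

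1. A participant finds a test painful and wants it to stop. Section 2.1 offers withdrawal of consent.
2. Section 7.6 applies. Data to that point stay, and a reason is recorded only if volunteered.
3. The questionnaire is due at the end of the appointment (7.5.5), after step 2. No section says whether it is given to this person.
4. The data set is incomplete, so recruitment continues (6.3) and a completer takes the place.

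Step 3 is where the loss becomes likely rather than certain.

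**Illustration 1: tolerability among starters**

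Assume that 90% of completers rate a test tolerable, that a proportion d of starters stop for discomfort without a rating, and that such a stop counts as not tolerated. Tolerability among starters = 0.90 × (1 − d).

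| d (assumed) | Calculation | Among starters | Reported from completers |
|---|---|---|---|
| 5% | 0.90 × 0.95 | 85.5% | 90% |
| 10% | 0.90 × 0.90 | 81% | 90% |
| 20% | 0.90 × 0.80 | 72% | 90% |

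**Illustration 2: counts with 30 completers**

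Let x of 30 completers report intolerance and k further participants stop unrated. The observed share is x/30. The share among starters is (x + k)/(30 + k).

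| k (assumed) | x = 0, observed 0% | x = 3, observed 10% |
|---|---|---|
| 1 | 1/31 = 3.2% | 4/31 = 12.9% |
| 3 | 3/33 = 9.1% | 6/33 = 18.2% |
| 5 | 5/35 = 14.3% | 8/35 = 22.9% |
| 8 | 8/38 = 21.1% | 11/38 = 28.9% |

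**Would it arise in a study this small?** At an assumed stop rate of 5%, the chance of at least one stop among 30 is 1 − 0.95^30 = 78.5%. To obtain 30 completers at stop rates of 5%, 10% and 20%, enrolment must be 30/0.95, 30/0.90 and 30/0.80, which round up to 32, 34 and 38.

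Both illustrations assume that no one who stops is rated. If some of them do complete the form, the gap shrinks accordingly.

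**The case against.** The strongest reply is that the loss is not written anywhere. Sections 1.0 and 7.5.5 speak of participants in general, and no section withholds the form from someone who stopped a test. In Procedure B the barostat comes first, so a person who stops it can still have the standard-care tests and reach the end of the visit. In Procedure A the barostat is last, so stopping it is the end of the visit. Section 2.1 can also be read as a reminder of a right rather than an instruction to process every stop as withdrawal. This stands, and it is why the point is about a likely loss. A reader might infer that those who could not tolerate a test are certainly absent from the outcome; the documents do not go that far.

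A reader might also infer that the team could not tell which test caused a drop-out. The documents do not support that. Section 3.3 counts drop-outs, the identification log in 7.2.2 records when and why someone withdrew, volunteered reasons go to the CRF (7.6), adverse events are logged (9.0), and the allocated order is on file (7.4). These sources are incomplete, because the reason is optional and identifiable information may be destroyed after withdrawal, but they are not empty. Nor do they supply a tolerability rating.

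A third tempting reading is that one form at the end of the visit is itself flawed, because of recall and because the last test differs between procedures. Order is already randomised to deal with order effects, and a single form lets participants compare the tests. Asking after each test would be a preference, not the correction of an error.

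Finally, the percentages above are assumed, the questionnaire is not shown, and the denominator may be set in an analysis plan that is not at hand. That limits what can be said about size. It does not supply a route for collecting the data.

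**Conclusion.** The point holds as a likely gap in data collection. The protocol states no way to obtain tolerability from a participant who stops a test, and sections 2.1, 6.3, 7.5.5 and 7.6 together favour losing that person from the outcome and replacing them with a completer. The tolerability figure could therefore be too favourable.

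The size is unknown. It depends on three things that the protocol does not give: how many participants stop for discomfort, how many of them are still offered and complete the form, and the share of completers who rate the test tolerable. Under the assumptions shown, a reported 90% would correspond to between 85.5% and 72% among starters. This is a cheap improvement that should be made, because it protects an outcome on which the feasibility objective depends.

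**What to change.** The change concerns recording and reporting only. It alters no rule on when a test is stopped.

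- **Sections 2.1 and 7.6:** record in the CRF that the participant asked to stop a test (which test, at what stage, and the reason if given) separately from withdrawal of consent to the study.
- **Section 7.5.5:** state that the questionnaire is also offered to those who stopped a test but have not withdrawn from the study.
- **Reporting:** give tolerability of each test over all participants who started it, counting a stop for pain or discomfort as not tolerated. Recruitment to complete data sets under 6.3 can continue, but those replaced stay in this denominator.

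The cost is one CRF field, brief wording and a protocol amendment. Under section 11.2 the amendment needs approval by the investigators, study team and sponsor, and by the ethics committee if it is classed as major. The tolerability figure may also come out less favourable.
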